Background: Structured diabetes self-management education (DSME) is internationally recommended for all people with newly diagnosed type 2 diabetes and is designed to support patients in self-managing their condition and prevent associated long-term complications. DSME is proven to be as effective as pharmacotherapy in preventing diabetes associated morbidity and premature mortality but attendance at both a national and local level remains poor. Local records suggest that of those that start DSME (9%) only 12.6% complete the programme. Attendance at DSME is currently benchmarked as having completed a registration form and had at least one active engagement with a programmes content, with 'completion' measured against ≥60% completion despite landmark trials reporting outcomes based on the full completion of a programme. Little is known, of the effectiveness of DSME on the psychological and emotional health of people with diabetes who complete less than the full DSME programme.

Aim: This feasibility study will test the impact of differing completion rates of a face-to-face DSME programme on patient reported outcomes measuring self-care, diabetes distress and quality of life in people with type 2 diabetes.

Methods: Using a quantitative approach, a single centre, randomised feasibility study will be conducted, aiming to recruit 120 eligible people with type 2 diabetes due to attend a secondary care diabetes clinic in the Northwest UK for specialist support, education and advice. Participants will be randomised into one of four groups: Group 1 will receive a full DSME programme, Group 2 will receive 60%, Group 3 will receive 10% and Group 4 will have delayed education. Normal clinical care will continue. Preliminary outcomes (psychometric questionnaire scores measuring ability to self-care, diabetes distress and health related quality of life) will be evaluated at baseline and 3-4 months post-intervention. Measures of feasibility (eligibility, recruitment and retention rates) will be

reported.

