- Group 3: DSME 36 minutes, 10% of content (attended)
- Group 4: Delayed education (education not offered, not attended, or declined)

DSME programme overview is provided in appendix 1 giving a broad overview of DSME content by programme completion status. Local demographic data suggests that of the local population 46.4% are living in the most deprived neighbourhoods within the UK (9). Of the local population 19.3% have a reading age of 9-11 or below (53,54), are classed as being functionally illiterate and are therefore likely to struggle reading a paper questionnaire. Verbal support for completing the PROMs will be offered by the researcher to ensure participants from lower socioeconomic backgrounds are not excluded from participating in the DIABETES PRO study as they are evidenced to make up a larger proportion of people with diabetes (55-57). Support will be limited to reading the questions verbatim.

Participants will be asked to complete three psychometric tests measuring self-care activities, diabetes distress and quality of life using the following validated tools: Diabetes Self-Management Questionnaire-Revised (DSMQ-R)(48), Problem Areas in Diabetes (PAID) scale (49) and the Patient Reported Outcome Measures Information System (PROMIS) Global Health scale v1.2 (50) (appendix 1).

Participants in groups 1, 2 and 3 will be asked to book a DSME session with the researcher, typically this should be no longer than 3 weeks from study enrolment. Research group DSME programmes (intervention) will be run by the researcher separate to routine patient DSME to minimise disruption of participants leaving part way through on patients.

Participants randomised to group 4, delayed education will not be required to attend DSME as part of the DIABETES PRO study. Collected data will be collected and managed using Research Electronic Data Capture (REDCap) electronic data capture tools. A REDCap data collection tool has been included in Appendix 1 for reference. REDCap is a secure, web-based software platform designed to support data capture for research studies, providing an intuitive interface for validated data capture; audit trails for tracking data manipulation and export procedures; automated export procedures for seamless data downloads to common statistical packages; and procedures for data integration and interoperability with external sources (58,59) (see section 3.6 for further details).

Visit 2

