Patient group 
 • Who is receiving the intervention? • How many patients are being seen? • Characteristics of the patients? 	
Patients with type 2 diabetes referred to the Diabetes Centre, St Helens Hospital for specialist intervention and / or DSME and / or registered with a St Helens GP and opted into data sharing will be screened for entry.
 
The Diabetes department works closely with primary care colleagues to offer specialist advice, education, and guidance to patients with diabetes who are assessed and then discharged for clinical management by their GP. Referrals for DSME are made directly from primary care into DSME education sessions. The shared care report highlights any patient with a local GP who has had a first use of a type 2 diabetes code within the last month and have opted into data sharing. The use of the three recruitment streams for this study allows for a sample which is representative of the local population and is not limited to only patients requiring specialist led care.
 
The DIABETES PRO study will aim to recruit 120 participants which will be randomised across four groups containing 30 participants each.
 
Patients ≥18 years of age from a variety of socioeconomic backgrounds. St Helens has a predominantly white British population (96.5%), and this is likely to be represented in the sample (37).

Workforce and staffing 
 • Staffing skill, grade and 	
The researcher is employed by the Diabetes Centre as a clinical research fellow and is a Fellow of the HEA with experience teaching

profession • Staff new or existing • Training needed to deploy the intervention?	adult learners within higher education settings. The researcher has a clinical background as a podiatrist and is currently registered with the HCPC. The researcher is the patient education lead within the department and is in the process of accrediting the DSME programme with QISMET.

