6.4 Data Analysis

Descriptive analysis will be completed for all demographic data presenting continuous variables as means \pm standard deviation and categorical variables as numbers (%). Data will be tested for normality using a Shapiro-Wilk test and subject to visual inspection of histograms and normal Q-Q plots.

Psychometric outcomes will include the Diabetes Self-Management Questionnaire-Revised (DSMQ-R)(48), Problem Areas in Diabetes (PAID) scale (49) and the Patient reported outcome measures information system (PROMIS) Global Health scale v1.2 (50). Data will be treated as continuous and analysis of the difference in the mean before and after intervention will be conducted using an analysis of variance (ANOVA) test to check for statistical and clinical difference in the mean across the four groups.

Statistical analysis will be conducted using IBM® SPSS® Premium 29 with support from University of Liverpool statisticians. The alpha level will be set at 5% for statistical significance.

Whilst a statistically significant difference is desirable, it is important to understand what would represent a meaningful clinical change for a patient. As such the minimal clinically important difference (MCID) will be reported to measure the smallest difference in which the patient would perceive a benefit (61–64). Where the MCID is not published this will be calculated using a distribution-based derivation using 0.5 SD of the observed change in PROM score (62,65). Whilst this approach is not without its limitations (61,63) no consensus on the ideal means of determining the MCID is available (63). A systematic review concluded that 0.5 SD of the observed change approximated the published MCID in the majority of cases popularising this derivation in the literature (65).

MCID will be classed as >2 T-score points for the PROMIS Global Health v1.2 (66) in which physical health and mental health are given separate T-scores with a 95% confidence interval. The MCID will be calculated for PAID and DSMQ-R.

Recruitment of participants and the number of dropouts will be reported descriptively (frequencies and percentages). Due to the aims of this study considering differing completion levels of DSME, intention to treat analysis will not be used. Where participants allocated to a group do not fully complete the required amount of DSME there results would be withdrawn from the final analysis.

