8.1.2 Exclusion Criteria

The following patients will be excluded entry into the study:

- Lack capacity to make an informed decision.
- A diagnosis of type 1, type 3c, Maturity-onset diabetes of the young (MODY) or gestational diabetes.

- Received structured education for their diabetes within the last 12 months either online or face to face.
- Require 1:1 education support e.g., requires interpreter.
- Patients unable to attend for structured classroom education e.g., housebound.

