8.2 Recruitment

8.2.1 Sample Size

A sample size of 24-50 participants per group is deemed adequate within a feasibility study to estimate effect sizes and inform future DSME modifications and research (68,69). A sample of 120 patients will be enrolled onto this study allowing for adequate numbers (n=30) across the four groups, controlling for expected participant drop out. Monthly recruitment targets are pre-specified in a study progression criteria table (table 3) to ensure an adequate sample size is achieved for data analysis.

The diabetes outpatient department receives on average 24 referrals for DSME per month with a mean monthly attendance rate of 21 patients. Locally an average of 86 patients are newly diagnosed with type 2 diabetes each month (20), patients who have opted in for data sharing are contacted with an offer of DSME. This has been used to inform realistic recruitment rates. Recruitment rates will be kept under review and discussed with supervisors should the monthly figure fall below projected numbers.

Table 3:Progression criteria and study status

Criterion	Green	Amber	Red
Monthly recruitment	≥ 17 participants	14-16 participants	< 13 participants
Retention rate	>80% at endpoint	60-80% at endpoint	<60% at endpoint

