8.2.21.2.2 Sample identification and technique

A convenience sample of 120 participants will be recruited for this study through three existing streams with potentially eligible participants added to the screening log sheet (appendix 1) and the pre-visit 1 section of the DIABETES-PRO study visit 1 pathway will be completed (appendix 1).

1. Clinic lists of new patients due to attend the diabetes centre at St Helens Hospital are available on the hospital patient administration system. The hospital electronic record will be used to screen for potentially eligible participants from the clinical list by the researcher. Potentially eligible participants due to attend new patient clinic will be invited into the study by letter (appendix 1, NP clinic screening letter) with attached PIS which will be posted ahead of their clinical appointment. On the day of their clinical appointment the researcher will meet potentially eligible participants to check they received the PIS and to answer any questions. Where potentially eligible participants agree they will be invited for

screening. Following screening, where eligible participants agree to be involved in the research and provide written informed consent, they will be enrolled in the study.

2. Patients who have been referred by their GP for DSME are called and offered education. Education referrals will be used to screen for potentially eligible participants from those awaiting a DSME appointment by the researcher. Potentially eligible participants will be asked as part of the DSME booking process if they would like information on the research. Where potential eligible participants agree a letter (appendix 1, telephone screening letter) will be sent out with a PIS and a screening appointment will be made with the researcher. Screening appointments will be offered either at the Diabetes Centre or as a home visit. Following screening, where eligible participants agree to be involved in the research and provide written informed consent, they will be enrolled in the study.

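### Education outside the study before Visit 3 is neither addressed for Groups 2 to 4 nor linked to the study data, and section 6.4 has no rule for participants who receive more DSME than allocated

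*Combined protocol and SAP*

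**What the plan says.** **Control arm.** Section 6.2 labels Group 4 as delayed education and adds that "Participants randomised to group 4, delayed education will not be required to attend DSME as part of the DIABETES PRO study". The full programme is offered to Groups 2, 3 and 4 when the study ends, and Table 4 expects access to be put back by up to four months.

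**Care in the meantime.** The Abstract states: "Normal clinical care will continue". Table 2 in section 6.2 states: "Referrals for DSME are made directly from primary care into DSME education sessions". In the second recruitment stream (section 8.2), "Patients who have been referred by their GP for DSME are called and offered education", and the study is raised during that booking process. The third stream works in the same way.

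**Earlier education.** Section 8.1.2 excludes anyone who "Received structured education for their diabetes within the last 12 months either online or face to face".

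**Follow-up data.** Visit 3 in section 6.2 is described only as repeating the baseline questionnaires: 3 to 4 months after the intervention, or 4 months after enrolment for Group 4.

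**Existing records.** Table 4 says that the service already logs DSME offers and attendance, with national reporting, and that the database is checked weekly. The stated purpose of that check is to avoid delay in offering DSME once the research is over.

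**Analysis.** Section 6.4 rules out intention to treat because the aims concern completion level, and then says: "Where participants allocated to a group do not fully complete the required amount of DSME there results would be withdrawn from the final analysis".

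**The concern.** Once the plan gives up analysis as randomised in favour of groups defined by exposure, exposure has to be known in both directions. Section 6.4 looks in one direction only. For Group 4 the required amount is zero, so nobody in that arm can fall short of it. A Group 4 participant who takes a course in month 2 stays in the analysis as unexposed, and a Group 3 participant who does so is still counted at 10%.

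Both stated comparisons are exposed to this. Education in Group 4 narrows 10% versus delayed education. Outside education in Group 2 narrows 60% versus 100%, which favours the conclusion that the two are equally effective. The plan itself treats online and face-to-face education in the 12 months before entry as important enough to exclude people, but the text does not repeat the check over the months in which the contrast forms.

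A feasibility study should also tell the full trial whether a delayed-education arm can be held for four months. The Abstract lists eligibility, recruitment and retention as its feasibility measures, and Table 3 has criteria for recruitment and retention only.

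**Working it through.** **1. The plan's own figure.** The sample size reproduces: 4 × 30 = 120. Recording outside education does not change it. The plan has no contamination allowance to reproduce.

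**2. Three questions put to the text.**
- *Is outside DSME restricted before Visit 3?* The label, the four-month delay in Table 4 and the end-of-study offer all point to an intended wait. The wording on attendance, continuing care and direct referral states no hold. The text does not settle the question.
- *Would it reach the study data?* The data listed in sections 6.2 and 6.3 are baseline characteristics and questionnaires. Local attendance is logged elsewhere for another purpose. Online education appears only as a pre-entry exclusion. The REDCap tool and visit checklists are in Appendix 1, supplied separately and not seen here.
- *Is there an analysis rule?* For too little DSME, yes. For too much, no.

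**3. How the bias behaves.** Everything in this step is an assumption used to show the range.

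Let E be the effect of the full programme, f the share of E gained from 36 minutes, and c3 and c4 the shares of Groups 3 and 4 who take a full course elsewhere and reach E.

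- Group 3 mean = fE(1 − c3) + c3E
- Group 4 mean = c4E
- True difference = fE

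*Only Group 4 affected:* the difference is (f − c4)E, so the share lost is c4/f.

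| f (assumed) | c4 (assumed) | Share of true difference lost |
|---|---|---|
| 0.5 | 0.091 × 0.126 = 0.0115 | 0.0115/0.5 = 2.3% |
| 0.5 | 0.091 | 0.091/0.5 = 18% |
| 0.5 | 0.25 | 50% |
| 0.5 | 0.50 | 100% |
| 0.1 | 0.10 | 100% |

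*Groups 3 and 4 equally affected (c3 = c4 = c):* the difference is f(1 − c)E, so the share lost is c. At c = 0.091 that is 9.1%, and the sign cannot reverse.

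*60% versus 100%:* if 60% of the programme gives a share g of E, and a share c2 of Group 2 completes the programme elsewhere, the difference falls from (1 − g)E to (1 − g)(1 − c2)E. The share lost is c2.

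**4. Why the local figures do not fix c.** The 9.1% in Table 1 is attendance within 12 months of diagnosis, not completion within 4 months. Section 2 (Background) says that 12.6% of local starters complete. Their product, 1.1%, is still a 12-month figure for newly diagnosed people in routine care, not for people who have consented to a trial of education. It also ignores any benefit from part-attendance.

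**5. Consequence for the later trial.** For full programme versus control, dilution by c multiplies the required sample size by 1/(1 − c)². At an assumed c of 20% this is 1/0.8² = 1.56, and at 30% it is 1/0.7² = 2.04. The full trial therefore needs an estimate of c.

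**The case against.** A reader might infer that outside education goes unrecorded and that nobody would know of it. The documents do not support that for routine local DSME. The centre is itself the provider (note to the study flow chart), the researcher is its patient education lead (Table 2), and Table 4 says that offers and attendance are logged. What remains is the missing link from that log to the study data, and online education.

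A reader might also infer that routine access stays open to Group 4, or that the arm is meant as a no-education control. Neither is stated. The arm is delayed education, a wait is clearly intended, and Table 4 mentions a routine waiting list that may limit uptake within four months. The participant information sheet, also in Appendix 1, may ask participants to wait. The fair criticism is silence, not open access.

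On size, it is tempting to use 9.1% as the share completing a course elsewhere, or to use section 8.2.1: "The diabetes outpatient department receives on average 24 referrals for DSME per month with a mean monthly attendance rate of 21 patients". The ratio 21/24 = 87.5% compares two monthly averages that need not describe the same patients. It concerns people being routinely booked, not people randomised to wait. Neither figure is a contamination rate. Sign reversal arises only if Group 4 is contaminated more than Group 3 and c4 is large relative to f.

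Finally, the study is declared unpowered, and holding the delayed arm is not among its declared feasibility measures, so reporting it is an addition and not an unmet commitment. That stands. The gap in section 6.4 does not depend on it.

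**Conclusion.** The point holds on the protocol text in this form. Whether Groups 2 to 4 may take up DSME elsewhere before Visit 3 is not stated. Bringing such education into the study data is not stated. Section 6.4 has no rule for participants who receive more than allocated, so following it as written analyses them at the lower level.

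The expected direction is towards no difference in 60% versus 100%, and in 10% versus delayed education when Group 4 is affected at least as much as Group 3. This assumes that outside education helps. The size is unknown. The illustrations run from about 2% of the true 10% versus delayed-education difference to all of it, depending on assumed values of c and f that the documents do not supply.

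If the Appendix 1 forms already ask about outside education, the data gap closes and only the reporting and the analysis rule remain. This should be put right before follow-up begins, because online education could not be reliably recovered later. It is not a reason to change the sample size or the visit schedule.

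**What to change.** 1. Unless Appendix 1 already contains it, add one item to the Visit 3 checklist and REDCap form for all four groups: any structured diabetes education outside the study since Visit 1, online or face to face, with date and approximate hours. Check the answer against the centre's existing DSME attendance record.
2. Report the result by group as a feasibility outcome.
3. State in section 6.4 how participants who receive more than allocated are handled: an analysis by randomised group, with a sensitivity analysis by education actually received for the two stated comparisons. The second is not protected by randomisation and should be labelled so.
4. Reconcile the attendance wording for Group 4 in section 6.2, the continuing-care statement in the Abstract and the four-month delay in Table 4, so that it is clear what happens to a routine referral or booking during follow-up. Which of these applies is for the sponsor and investigators to decide.

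Cost: one question at an existing visit, a look-up in records already kept, one added table and a slightly longer Visit 3.

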6.3 Data Collection

A REDCap data capture template has been created for collection and analysis and included in Appendix 1. REDCap which provides a secure platform for clinical research studies (58,59) will be utilised for data capture. Screening and baseline demographics will be obtained from the patient electronic record system, if any demographic information is unavailable this will be collected direct from the participant. Paper questionnaires will be completed by hand by study participants supported by the researcher and subsequently entered on the

data capture sheet by the researcher (example data capture template in appendix 1). To ensure consistency of the data being collected DIABETES-PRO pathway checklists will be used for visits 1, 2 and 3 (appendix 1).

6.4 Data Analysis

Descriptive analysis will be completed for all demographic data presenting continuous variables as means \pm standard deviation and categorical variables as numbers (%). Data will be tested for normality using a Shapiro-Wilk test and subject to visual inspection of histograms and normal Q-Q plots.

Psychometric outcomes will include the Diabetes Self-Management Questionnaire-Revised (DSMQ-R)(48), Problem Areas in Diabetes (PAID) scale (49) and the Patient reported outcome measures information system (PROMIS) Global Health scale v1.2 (50). Data will be treated as continuous and analysis of the difference in the mean before and after intervention will be conducted using an analysis of variance (ANOVA) test to check for statistical and clinical difference in the mean across the four groups.

Statistical analysis will be conducted using IBM® SPSS® Premium 29 with support from University of Liverpool statisticians. The alpha level will be set at 5% for statistical significance.

Whilst a statistically significant difference is desirable, it is important to understand what would represent a meaningful clinical change for a patient. As such the minimal clinically important difference (MCID) will be reported to measure the smallest difference in which the patient would perceive a benefit (61–64). Where the MCID is not published this will be calculated using a distribution-based derivation using 0.5 SD of the observed change in PROM score (62,65). Whilst this approach is not without its limitations (61,63) no consensus on the ideal means of determining the MCID is available (63). A systematic review concluded that 0.5 SD of the observed change approximated the published MCID in the majority of cases popularising this derivation in the literature (65).

MCID will be classed as >2 T-score points for the PROMIS Global Health v1.2 (66) in which physical health and mental health are given separate T-scores with a 95% confidence interval. The MCID will be calculated for PAID and DSMQ-R.

Recruitment of participants and the number of dropouts will be reported descriptively (frequencies and percentages). Due to the aims of this study considering differing completion levels of DSME, intention to treat analysis will not be used. Where participants allocated to a group do not fully complete the required amount of DSME there results would be withdrawn from the final analysis.

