5.2 Outcome

The primary outcome measure will be measured as:

- Change in self-care activities outcome measure (pre and post intervention) using the Diabetes Self-Management Questionnaire - Revised (DSMQ-R) scale (48).

Secondary outcome data will capture data on:

- Change in diabetes distress (pre and post intervention) using the Problem Areas in Diabetes (PAID) tool (49).
- Quality of life outcome measures (pre and post intervention) using the PROMIS-Global Health V1.2 scale (50).

Other preliminary data will explore whether deprivation and diabetes duration have any impact on PROMs across the four groups.

STUDY DESIGN AND METHODS OF DATA COLLECTION

This is a quantitative feasibility study focusing on the impact of differing completion rates of DSME programmes on psychometric outcomes pre and 4 months post intervention.

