Intervention • How is the intervention different from normal care? • What does it look like? • Is it clear when it starts and finishes?	Clinical intervention of participants will not be altered. Participants will receive the same DSME programme as routine clinical patients. Normal delivery of DSME programmes is by a diabetes specialist nurse or dietitian. Research DSME programmes will be, where possible, delivered by the researcher for consistency. Participants will be reminded at the beginning of the DSME programme that this is a research study and that some participants will leave after 36 minutes, 3 hours and 36 minutes, with others remaining for the full 6 hours programme. Reminders will be given at the time points in which participants from groups 2 and 3 should leave.
Contextual information • Policy initiatives related to the intervention?	DSME is NICE recommended for all patients newly diagnosed with type 2 diabetes with annual refresher thereafter (15). The National Diabetes Audit suggests 71% of people with type 2 diabetes are offered DSME, with an average attendance rate of 7%. Local records suggest that of those that start DSME (9%) only 12.6% complete the programme (20).

Visit 3

Between 3-4 months post intervention participants will be asked to repeat baseline psychometric tests. For participants in group 4 this will be 4 months from enrolment. This will be the end of the study.

At the end of the study participants in groups 2, 3 and 4 will be offered a full DSME programme.

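### Optional gain in precision: section 6.4 uses the baseline PROM score only for subtraction, and adding it as a covariate would usually narrow the group contrasts

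*Combined protocol and SAP*

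**What the plan says.** Section 5.2 defines the primary outcome as change on the DSMQ-R: "Change in self-care activities outcome measure (pre and post intervention"). Change in PAID and the PROMIS Global Health measures are secondary.

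Under section 6.2, all three instruments are completed at Visit 1 and again at Visit 3: "Between 3-4 months post intervention participants will be asked to repeat baseline psychometric tests". Every analysed participant should therefore have a baseline and a follow-up value of each score.

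Section 6.4 treats the scores as continuous and specifies "analysis of the difference in the mean before and after intervention will be conducted using an analysis of variance (ANOVA") across the four groups, with alpha at 5%. For DSMQ-R and PAID it derives the minimal clinically important difference (MCID) from the data: "this will be calculated using a distribution-based derivation using 0.5 SD of the observed change in PROM score". PROMIS is scored as two outcomes, "in which physical health and mental health are given separate T-scores with a 95% confidence interval".

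The same section rejects intention to treat: "Where participants allocated to a group do not fully complete the required amount of DSME there results would be withdrawn from the final analysis".

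No section mentions ANCOVA or baseline adjustment. Section 5.2 proposes to explore deprivation and diabetes duration, which is a different question from adjusting for the baseline score.

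**The concern.** A baseline score can do more than be subtracted. Subtraction fixes the slope of follow-up on baseline at 1; ANCOVA estimates it. When the true slope differs from 1, the change score keeps avoidable noise and the interval for each group contrast is wider than it need be.

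Precision is a fair yardstick here. Section 6.1 says that the study is not statistically powered, and section 8.2.1 justifies its size by estimation: "A sample size of 24-50 participants per group is deemed adequate within a feasibility study to estimate effect sizes". The contrasts in the aim (10% of the programme against none, 60% against 100%) will be read from their estimates and intervals, and those estimates may inform the full trial that this study is meant to prepare. What is at stake is interval width. Bias and the validity of the test are not in question, and neither progression criterion in Table 3 (recruitment, retention) depends on PROM precision.

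**Working it through.** **Plan's own figure.** The documents state no power, SD, effect size or precision target, so there is no formula-based figure to reproduce. The arithmetic of the sample size agrees: 4 × 30 = 120.

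**Inputs from the documents.** Four groups of 30 (Study Summary; 8.2.1). Section 6.2 describes the randomisation blocks as 2:1, which does not fit four equal groups; equal groups are used here. Alpha is 5% (6.4), taken as two-sided. A second case uses 24 per group = 30 × 0.80, from the 80% limit for green retention in Table 3; the loss rate is an assumption.

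**Inputs assumed.** Pre-post correlation r = 0.3 to 0.9. Baseline SD = 1. Follow-up SD = q times baseline, with q = 1 in the main case and q = 0.8 and 1.2 as alternatives.

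**Formulas.**
- Variance of change: 1 + q² − 2rq. At q = 1 this is 2(1 − r).
- ANCOVA residual variance: q²(1 − r²). At q = 1 this is 1 − r².
- The first minus the second is (1 − rq)², which is never negative. At q = 1 the variance ratio, ANCOVA to change, is (1 + r)/2.
- Half-width of a pairwise 95% interval, change score: t(0.975; 4n − 4) × √(variance × 2/n).
- The same for ANCOVA: t(0.975; 4n − 5), with the variance multiplied by 1 + 1/(4n − 6) for estimating the slope. The multiplier is 1.0088 at n = 30 and 1.0111 at n = 24.

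**Example, n = 30, q = 1, r = 0.5.** Change: 1.9806 × √(1.00 × 2/30) = 0.511. ANCOVA: 1.9808 × √(0.75 × 1.0088 × 2/30) = 0.445. Ratio 0.870, so 13% narrower.

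**Results, equal SDs** (half-widths in units of the score SD):

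| r | Variance ratio | n = 30: change → ANCOVA | Narrower | n = 24: change → ANCOVA | Narrower |
|---|---|---|---|---|---|
| 0.3 | 0.65 | 0.605 → 0.490 | 19% | 0.678 → 0.550 | 19% |
| 0.5 | 0.75 | 0.511 → 0.445 | 13% | 0.573 → 0.499 | 13% |
| 0.7 | 0.85 | 0.396 → 0.367 | 7% | 0.444 → 0.412 | 7% |
| 0.8 | 0.90 | 0.323 → 0.308 | 5% | 0.363 → 0.346 | 5% |
| 0.9 | 0.95 | 0.229 → 0.224 | 2% | 0.256 → 0.251 | 2% |

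With the slope cost counted, 30 per group under ANCOVA at r = 0.5 matches about 40 per group under change scores. The break-even is r of about 0.98 at either size.

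**Unequal SDs** (variance ratio before the slope cost, r = 0.3, 0.5, 0.7, 0.8):
- q = 0.8: 0.50, 0.57, 0.63, 0.64. The gain is larger.
- q = 1.2: 0.76, 0.87, 0.97, 0.997. At r = 0.8 the slope cost outweighs the saving: √(0.5184 × 1.0088 / 0.5200) = 1.003, so ANCOVA is about 0.3% wider.

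**Simulation.** With 3,000 trials per setting (equal SDs, no group effect), mean half-widths at n = 30 and r = 0.3, 0.5 and 0.7 were 0.603/0.487, 0.510/0.444 and 0.395/0.365. Across n = 30 and 24 and r = 0.3 to 0.9, type I error lay between about 4.5% and 5.5% for both methods.

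**Alternative reading of ANOVA.** If 6.4 means a repeated-measures, group-by-time model, its interaction test with two time points is the change-score ANOVA, so the result is the same.

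**The case against.** The strongest reply is that nothing is wrong. ANOVA on change matches the outcome in 5.2, is valid under randomisation, and serves preliminary outcomes in a study whose formal criteria are recruitment and retention. The size of the gain rests entirely on correlations and SDs that the documents do not supply; it is 2% at r = 0.9 and slightly negative in one plausible case. All of that stands. It makes the point optional but leaves the direction of the usual effect unchanged.

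A reader might infer a stronger point: that adjustment brings the half-width below the MCID and so makes the study able to resolve a clinically important difference. The documents do not support this. Section 6.4 sets no rule comparing an interval half-width with the MCID. Taking the MCID as 0.5 SD of change, the planned half-width is 1.9806 × √(2/30) / 0.5 = 1.02 MCID at every r, so a crossing at 30 per group starts only 2% above the line. ANCOVA is still at 1.001 MCID when r = 0.9. At 24 per group it is 0.999 at r = 0.5 and above 1 for higher r; at 20 per group it is above 1 at every r assumed. Section 8.2.1 says that the 30 already allows for dropout, and 6.4 removes further participants at an unknown rate.

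A reader might also infer that adjustment protects the comparison against the completers-only analysis. It does not. Non-completers are withdrawn, yet "Participants randomised to group 4, delayed education will not be required to attend DSME as part of the DIABETES PRO study", so group 4 has no education to fail to complete and the selection can differ between groups. If that unbalances baseline scores, the ANCOVA and unadjusted change-score estimates may differ in value as well as in width, and neither removes the selection.

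**Conclusion.** The point holds as an optional improvement. Section 6.4 leaves precision unused that data already collected could supply. With equal SDs, the pairwise intervals would be roughly 5% to 19% narrower for r between 0.8 and 0.3, and about 2% narrower at r = 0.9. The proportional gain barely changes between 30 and 24 per group. It grows if scores become less variable at follow-up and can vanish if they become more variable.

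These sizes rest on assumed correlations and SDs, equal group sizes, and groups still comparable at baseline. The planned analysis is not invalid, no progression decision depends on the change, and no claim about reaching the MCID follows from it.

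**What to change.** Replace the ANOVA sentence in 6.4 with wording such as: *Each of the four scores (DSMQ-R, PAID, PROMIS physical health T-score, PROMIS mental health T-score) will be analysed by ANCOVA, with randomised group as a factor and the baseline value of the same score as covariate. Adjusted mean differences between groups will be reported with 95% confidence intervals.*

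Change may remain the dependent variable: ANCOVA on change and ANCOVA on the follow-up score give identical group contrasts. The outcome in 5.2 and the MCID derivation in 6.4 therefore need no rewriting. That identity is between the two forms of ANCOVA; it does not extend to unadjusted change scores.

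The cost is one residual degree of freedom per model (115 instead of 116 with 120 analysed), one covariate in each SPSS model and one sentence in 6.4. No extra data, visits or participants are needed. Specify it before the data are analysed, so that adjustment is not a post hoc choice. The exclusion of non-completers needs separate attention.
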